6.1 Accrual and sample size calculations

Recruitment will target enrolling 56 healthy, HIV-uninfected adult participants, aged 18 to 50 years.

To ensure that both men and women will be adequately represented in the trial, the trial will enroll at least approximately 40% of each sex overall. Hence, when approximately 33 participants of one sex are enrolled, recruitment of persons born of that sex will stop.

Since enrollment is concurrent with receiving the first study vaccination, all participants will provide some safety data. However, for immunogenicity analyses, it is possible that data may be missing for various reasons, such as participants terminating from the study early, problems in shipping specimens, low cell viability of processed peripheral blood mononuclear cells (PBMCs) or high background. Immunogenicity data from 17 phase 1 and 2 phase 2a HVTN vaccine trials, which began enrolling after June 2005 (data as of September 2014), indicate that 17% is a reasonable estimate for the rate of missing data at day 182. For this reason, the sample size calculations in Section 6.1.2 account for 4 enrolled participants receiving vaccine having missing data for each study arm at the primary immunogenicity endpoint.

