6.1.2 Sample size calculations for immunogenicity

For comparing the CD4+ and CD8+ T-cell endpoints between the 2 vaccine regimens, the primary analysis uses head-to-head superiority comparisons. The comparison will be performed separately for each of the primary breadth and secondary magnitude T-cell subset endpoints. No multiplicity adjustments are made for the multiple comparisons given the utility to favor higher power at the expense of a higher accepted false positive rate.

Figure 6-1 below summarizes power available for superiority testing. For these calculations, we assume 17% missing data (n=21 evaluable endpoints from each arm). Sample size calculations for breadth of response are based on data from the HVTN 083 trial and assume a beta-binomial distribution. Sample size calculations for ICS magnitude assume normally distributed magnitudes after natural log transformation with standard deviation = 1. The assumptions for the sample size calculations for ICS magnitude are based on the data from the HVTN 080 trial. Superiority test power is based on the Mann-Whitney U test with 2-sided p-value <0.05 as statistically significant.

If mean CE breadth in the vaccine recipients in Group 1 is 0.2 (0.5) then the study has 80% power to detect superiority in Group 2 if the true CE breadth the 2^{nd} group is at least 1.0 (1.5). A 2.5 fold-change in the vaccine recipients from Group 2 versus Group 1 is required to have 80% power to detect superiority in the T-cell response magnitude.

[figure not shown]

Figure 6-1 Power to detect superiority in CE Breadth and ICS Magnitude. Power calculations for the breadth of response were run under two different scenarios. In the first panel power the mean CE Breadth is assumed to be 0.2 for the vaccine recipients in Group 1 while the second panel assumes a mean CE Breadth of 0.5. In the third panel power calculations are shown for the magnitude of response. The x-axis in the first two panels is the CE Breadth for the vaccine recipients in Group 2 and for the third panel it the x-axis is the fold change in ICS response magnitude for vaccine recipients from Group 2 versus Group 1. Power curves are shown for N=20, 25, and 30 vaccine recipients per Group and account for 17% missing immunogenicity data.

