The analysis of CD4⁺ and CD8⁺ T-cell response rates as measured by the ICS assay will be evaluated and compared as described under the general approach. For each T-cell subset, the positivity call for each peptide pool will include a multiple comparison adjustment for the number of peptide pools used in the assay. In general, the Mixture Models for Single-cell Assays (MIMOSA) statistical framework [96] and/or the Fisher's exact test-based positivity criteria will be used. Details of the positivity criteria will be discussed in the SAP. The magnitude of marginal response will be analyzed as described for quantitative data in the general approach section. For each T-cell subset, graphs will be used to display the background-subtracted magnitudes for each participant by protein, treatment arm and timepoint. Statistical testing comparing the magnitudes will be based on positive responders only. The polyfunctionality of ICS responses will also be analyzed as a secondary endpoint. Besides descriptive plots of the magnitude of polyfunctional responses, the COMPASS (Combinatorial Polyfunctionality analysis of Antigen-Specific T-cell Subsets) statistical framework will also be used to perform joint modelling of

multiple T-cell subsets of different cytokine combinations using the functionality score (FS) and the polyfunctionality score (PFS) to summarize the multi-parameter ICS responses.

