10.2 Intracellular Cytokine Staining Assay (ICS)

HIV-1-specific CD4+ and CD8+ T-cell responses are measured by intracellular cytokine staining as previously described (De Rosa, 2012 & Horton, 2007). A validated 28-color panel (experiment Assay ID 114; analysis plan 048) is used to evaluate Gag CE total and Gag p55 peptides at visit 6 (month 1.5/2 weeks post 2nd vaccination) and visit 11 (Month 6.5/2 weeks post 4th vaccination). CD4+ and CD8+ T cells expressing IL-2 and/or IFN- γ are included in the primary analysis. Marginal expression of CD40L for CD4+ T cells are included as a secondary analysis.

Several criteria are used to determine if data from an assay were acceptable and could be statistically analyzed. The blood draw date must have been within the allowable visit window as determined by the protocol. Post-infection samples from HIV-infected participants are excluded. After sample thawing and overnight incubation, the viability of the PBMC must have been 66% or greater for testing to have proceeded. If it was not, a new specimen for that participant at that time point was thawed for testing. If the PBMC viability of the second thawed aliquot was below this threshold, the ICS assay was not performed and no data were reported to the statistical center for the participant-time point. For the negative control acceptance criteria, if the average cytokine response for the negative control wells was above 0.1% for either the CD4+ or CD8+ T cells, the sample was retested. If the retested results were above 0.1%, the data were excluded from analysis; otherwise, the retest data were used.

The total numbers of CD4+ and CD8+ T cells must also have exceeded certain thresholds. If the number of CD4+ T cells was < 10,000 or the number of CD8+ T cells was < 5,000 for any of the HIV-1 peptide pools or for one of the negative control replicates for a particular sample, data for that stimulation were filtered. If both negative control replicates failed for number of T cells, the sample was retested. If one negative control replicate failed for number of T cells, the negative control replicate with sufficient cells was used.

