To assess positivity for a peptide pool within a T-cell subset, a two-by-two contingency table was constructed comparing the HIV-1 peptide stimulated and negative control data. The four entries in each table were the number of cells positive for IL-2 and/or IFN- γ and the number of cells negative for IL-2 and IFN- γ for both the stimulated and the negative control data. If both negative control replicates were included, then the average number of total cells and the average number of positive cells were used. A one-sided Fisher's exact test was applied to the table, testing whether the number of cytokine-producing cells for the

stimulated data was equal to that for the negative control data. Since multiple individual tests (for each peptide pool) were conducted simultaneously, a multiplicity adjustment was made to the individual peptide pool p-values using the Bonferroni-Holm adjustment method. If the adjusted p-value for a peptide pool was ≤ 0.00001 , the response to the peptide pool for the T-cell subset was considered positive. Because the sample sizes (i.e., total cell counts for the T-cell subset) were large, e.g., as high as 100,000 cells, the Fisher's exact test has high power to reject the null hypothesis for very small differences. Therefore, the adjusted p-value significance threshold was chosen stringently (≤ 0.00001). If at least one peptide pool for a specific HIV-1 protein was positive, then the overall response to the protein was considered positive. If any peptide pool was positive for a T-cell subset, then the overall response for that T-cell subset was considered positive.

The following comparisons of the immune response rates and magnitudes (among positive responders only) will be done:

- Fisher's exact test and Barnard's test are used to compare response rates between pairs of groups, and the Wilcoxon rank sum test is used to compare response magnitudes among positive responders between pairs of groups. Group comparisons include T1 vs. control (pooled), T2 vs. control (pooled), and T1 vs. T2. P-values are two-sided and unadjusted for multiple comparisons.

Contingent upon these results, additional assays and/or analyses may be performed.

The following comparisons of FS and PFS will be done:

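### The stated 80% power for a 2.5-fold ICS magnitude difference counts all 21 evaluable vaccinees per arm, but the planned test uses positive responders only

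*Protocol*

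**What the plan says.** Protocol 6.1.2 powers the ICS magnitude comparison with a two-sided Mann-Whitney test at 0.05, taking magnitudes as normal on the natural-log scale with SD 1. On the number of participants it says: "For these calculations, we assume 17% missing data (n=21 evaluable endpoints from each arm". Section 6.1 explains the reduction from 25: "the sample size calculations in Section 6.1.2 account for 4 enrolled participants receiving vaccine having missing data for each study arm". The caption of Figure 6-1 mentions the same single allowance: "Power curves are shown for N=20, 25, and 30 vaccine recipients per Group and account for 17% missing immunogenicity data". On the source of the inputs: "The assumptions for the sample size calculations for ICS magnitude are based on the data from the HVTN 080 trial". The result is the sentence "A 2.5 fold-change in the vaccine recipients from Group 2 versus Group 1 is required to have 80% power to detect superiority".

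The analysis sections define a narrower set for the test. Protocol 6.4.4.2, repeated in SAP 8.4.2, says: "Statistical testing comparing the magnitudes will be based on positive responders only". SAP 10.2 says: "The following comparisons of the immune response rates and magnitudes (among positive responders only) will be done". It names the Wilcoxon rank sum test for magnitude, and its list of tables makes that comparison conditional on at least 5 responders in each group at the visit. The assay "is used to evaluate Gag CE total and Gag p55 peptides at visit 6" and again at visit 11, so there are two antigens, each with its own response rate.

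**The concern.** A participant with a valid sample but a negative positivity call counts among the 21 evaluable, yet contributes nothing to the magnitude test. The loss from 25 to 21 covers early termination, shipping problems, low viability and high background. Non-response comes on top of these, and no response rate enters 6.1.2. So the number of observations powered is not the number that will be tested, unless essentially everyone responds.

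This is the only statement in 6.1.2 of what the magnitude comparison under secondary endpoint 1 can detect. A reader who relies on it could take a non-significant responders-only result as evidence against a 2.5-fold difference when the test had much less than 80% power to find one.

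**Working it through.** **Inputs.** From Protocol 6.1.2: Mann-Whitney test, two-sided 0.05; natural-log SD 1; shift ln(2.5) = 0.916; 25 − 4 = 21 per arm. From SAP 10.2: responders only, with at least 5 per group. Assumed, because the text gives neither: the response rate and the SD among responders.

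**Step 1: reproduce the stated figure.** Simulating the Mann-Whitney test with exact critical values, 21 per arm, SD 1 and shift 0.916 gives power 0.80. The arithmetic in 6.1.2 is therefore right for its inputs, and those inputs put all 21 per arm in the test.

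**Step 2: fixed numbers of responders, SD 1.**

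| Responders per arm | Power at 2.5-fold | Fold-change with 80% power |
|---|---|---|
| 21 | 0.80 | 2.5 |
| 17 | 0.71 | 2.8 |
| 13 | 0.57 | 3.3 |
| 10 | 0.45 | about 4 |
| 8 | 0.38 | 4.7 |
| 5 | 0.18 | about 10 |

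**Step 3: average over the number of responders.** In each arm the responder count is Binomial(21, p). Power = Σ over a, b ≥ 5 of P(a)·P(b)·power(a, b), counting zero when either arm has fewer than 5. The same p is used in both arms, and the true difference among responders is 2.5-fold.

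| Response rate | SD 0.75 | SD 1 | SD 1.25 | Comparison not run |
|---|---|---|---|---|
| 100% | 0.96 | 0.80 | 0.62 | 0% |
| 80% | 0.91 | 0.70 | 0.51 | 0% |
| 60% | 0.79 | 0.55 | – | 0% |
| 50% | 0.69 | 0.46 | 0.31 | under 1% |
| 30% | 0.31 | 0.19 | – | 36% |

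Further values at SD 1: 0.78 at 95% response, 0.75 at 90%, and 0.34 at 40% (not run in 7% of trials). With unequal rates at SD 1, 50% against 80% gives about 0.57 and 20% against 80% about 0.17.

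**Step 4: the SD that would rescue the claim.** For 2.5-fold to keep 80% power, the responder SD must be about 0.90 with 17 responders per arm, 0.76 with 13, 0.66 with 10 and 0.59 with 8.

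**Step 5: is near-complete response a safe assumption?** The breadth scenarios in 6.1.2 take a mean of 0.2 or 0.5 targeted CEs in one arm. Breadth is a count, so P(breadth ≥ 1) cannot exceed its mean. At most 20% or 50% of that arm then targets any individual CE, or at most 0.2 × 21 = 4.2 or 0.5 × 21 = 10.5 participants; the first is below the SAP minimum of 5. Rates to total CE or Gag p55 could be higher. Protocol 4.10.3 reports 42% to 82% response after DNA priming in another trial, but by ELISpot. Neither source gives a planning rate for this ICS comparison, and neither supports assuming 100%.

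**The case against.** There are four fair points on the other side.

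- **Missing figures.** Figure 6-1 and the HVTN 080 response plots (Figures 4-16 and 4-17) are not available in the text reviewed, and they may show response rates or responder-only magnitudes. It is right to say only that the text of 6.1.2 states no response rate. But the text and the Figure 6-1 caption attribute the 21 to missing data alone, so those figures cannot make it a responder count.
- **Two-part test.** The general approach (Protocol 6.4.4.1, SAP 8.4.1) allows Lachenbruch's statistic for ICS when a mixture model best describes the difference, and that statistic uses non-responders too. This limits the practical consequence. It is conditional, however, is not among the comparisons in SAP 10.2, and is not the test powered in 6.1.2.
- **Unknown SD.** If responders vary less than SD 1, the loss is smaller; Steps 3 and 4 show by how much. This stands as a limit on the size of the overstatement, not on the omission.
- **Low stakes.** The endpoint is secondary, the trial is a 56-person phase 1 study, and the SAP describes randomization and much of the ICS processing as already done. Restating power changes no estimate or test, and the 5-responder rule already withholds the weakest comparisons. That argues for a light remedy. It does not make the stated figure apply to the planned test.

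**Conclusion.** The concern holds. The 2.5-fold/80% statement is correct for 21 observations per arm but does not describe the responders-only test in Protocol 6.4.4.2 and SAP 10.2. It is too favourable unless nearly everyone in both arms responds or the SD among responders is below 1. At SD 1, power at 2.5-fold runs from 0.75 (90% response) through 0.46 (50%) to 0.19 (30%). These values assume log-normal magnitudes and equal response rates in the two arms. The size of the shortfall is a range, because neither the response rate nor the basis of the SD is stated in the text. It should be fixed. The primary breadth comparison is unaffected.

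**What to change.** Replace the single magnitude sentence in Protocol 6.1.2 with wording such as:

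> The magnitude comparison is made among positive responders. Assuming SD 1 on the natural-log scale among responders, the fold-change detectable with 80% power is 2.5 with 21 responders per arm, 2.8 with 17, 3.3 with 13, about 4 with 10 and about 10 with 5, the minimum at which the comparison is run.

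Alongside it, state the response rate and responder SD assumed for total p24CE and for Gag, and whether the HVTN 080 SD came from responders or from all participants. If it came from all participants, recompute the row of fold-changes with a responder SD.

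If the protocol is no longer being amended, put the statement in the SAP at the update that SAP section 1 already schedules before additional immunogenicity analyses. The cost is one sentence or a small table and a less favourable stated detectable difference. The test, sample size, assay and data collection stay as they are.

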6.2 Randomization

The randomization sequence will be obtained by computer-generated random numbers and provided to each HVTN CRS through a Web-based randomization system. The randomization will be done in blocks to ensure balance across arms. At each institution, the pharmacist with primary responsibility for dispensing study products is charged with maintaining security of the treatment assignments (except in emergency situations as specified in the HVTN MOP).

6.3 Blinding

Participants and site staff (except for site pharmacists) will be blinded as to participant treatment arm assignments (ie, blinded to both group and vaccine/control status). Study product assignments are accessible to those HVTN CRS pharmacists, DAIDS protocol

pharmacists and contract monitors, and SDMC staff who are required to know this information in order to ensure proper trial conduct. Any discussion of study product assignment between pharmacy staff and any other HVTN CRS staff is prohibited. The HVTN SMB members also are unblinded to treatment assignment in order to conduct review of trial safety.

When a participant leaves the trial prior to study completion, the participant will be told he or she must wait until all participants are unblinded to learn his or her treatment assignment.

Emergency unblinding decisions will be made by the site investigator. If time permits, the HVTN PSRT should be consulted before emergency unblinding occurs.

6.4 Statistical analyses

This section describes the final study analyses, unblinded as to treatment arm assignment. All data from enrolled participants will be analyzed according to the initial randomization assignment regardless of how many vaccinations they received. In the rare instance that a participant receives the wrong treatment at a specific vaccination time, the Statistical Analysis Plan will address how to analyze the participant's safety data. Analyses are modified intent-to-treat in that individuals who are randomized but not enrolled do not contribute data and hence are excluded. Because of blinding and the brief length of time between randomization and enrollment—typically no more than 4 working days—very few such individuals are expected.

Analyses for primary endpoints will be performed using SAS and R. All other descriptive and inferential statistical analyses will be performed using SAS, StatXact, or R statistical software.

No formal multiple comparison adjustments will be employed for multiple safety endpoints, multiple primary immunogenicity endpoints, or secondary endpoints. However, multiplicity adjustments will be made for certain immunogenicity assays, as discussed below, when the assay endpoint is viewed as a collection of hypotheses (eg, testing multiple peptide pools to determine a positive response).

6.4.1 Analysis variables

The analysis variables consist of baseline participant characteristics, safety, and immunogenicity for primary- and secondary-objective analyses.

6.4.2 Baseline comparability

Treatment arms will be compared for baseline participant characteristics using descriptive statistics.

6.4.3 Safety/tolerability analysis

Since enrollment is concurrent with receiving the first vaccination, all participants will have received at least 1 vaccination and therefore will provide some safety data.

6.4.3.1 Reactogenicity

The number and percentage of participants experiencing each type of reactogenicity sign or symptom will be tabulated by severity and treatment arm and the percentages displayed graphically by arm. For a given sign or symptom, each participant's reactogenicity will be counted once under the maximum severity for all injection visits. In addition, to the individual types of events, the maximum severity of local pain or tenderness, induration or erythema, and of systemic symptoms will be calculated. Kruskal-Wallis tests will be used to test for differences in severity between arms.

6.4.3.2 AEs and SAEs

AEs will be summarized using MedDRA System Organ Class and preferred terms. Tables will show by treatment arm the number and percentage of participants experiencing an AE within a System Organ Class or within preferred term category by severity or by relationship to study product. For the calculations in these tables, a participant with multiple AEs within a category will be counted once under the maximum severity or the strongest recorded causal relationship to study product. Formal statistical testing comparing arms is not planned since interpretation of differences must rely heavily upon clinical judgment.

A listing of SAEs reported to the DAIDS Regulatory Support Center (RSC) Safety Office will provide details of the events including severity, relationship to study product, time between onset and last vaccination, and number of vaccinations received. A separate listing will do the same for AEs of special interest (AESI). AESI for this protocol include but are not limited to autoimmune disorders; a sample list of AESI is provided in Appendix G.

6.4.3.3 Local laboratory values

Box plots of local laboratory values will be generated for baseline values and for values measured during the course of the study by treatment arm and visit. Each box plot will show the first quartile, the median, and the third quartile. Outliers (values outside the box plot) will also be plotted. If appropriate, horizontal lines representing boundaries for abnormal values will be plotted.

For each local laboratory measure, summary statistics will be presented by treatment arm and time point, as well as changes from baseline for post-enrollment values. In addition, the number (percentage) of participants with local laboratory values recorded as meeting Grade 1 AE criteria or above as specified in the Division of AIDS Table for Grading the Severity of Adult and Pediatric Adverse Events will be tabulated by treatment arm for each post-vaccination time point. Reportable clinical laboratory abnormalities without an associated clinical diagnosis will also be included in the tabulation of AEs described above.

6.4.3.4 Reasons for vaccination discontinuation and early study termination

The number and percentage of participants who discontinue vaccination and who terminate the study early will be tabulated by reason and treatment arm.

6.4.4 Immunogenicity analysis

6.4.4.1 General approach

For the statistical analysis of immunogenicity endpoints, data from enrolled participants will be used according to the initial randomization assignment regardless of how many injections they received. Additional analyses may be performed, limited to participants who received all scheduled injections per protocol. Assay results that are unreliable, from specimens collected outside of the visit window, or from HIV-infected participants postinfection are excluded. Since the exact date of HIV infection is unknown, any assay data from blood draws 4 weeks prior to an infected participant's last seronegative sample and thereafter may be excluded. If an HIV-infected participant does not have a seronegative sample postenrollment, then all data from that participant may be excluded from the analysis.

Discrete categorical assay endpoints (eg, response rates) will be analyzed by tabulating the frequency of positive response for each assay by antigen and treatment arm at each timepoint for which an assessment is performed. Crude response rates will be presented with their corresponding 95% confidence interval estimates calculated using the score test method [92]. Because of the small numbers of control participants in each group, no adjustment will be made to the vaccine arm estimates for the false positive rates in the control arms. Fisher's exact tests will be used to compare the response rates of any 2 vaccine arms, with a significant difference declared if the 2-sided p-value is ≤ 0.05 .

For quantitative assay data (eg, percentage of positive cells from the ICS assay or mean fluorescence intensity from the binding antibody multiplex assay), graphical and tabular summaries of the distributions by antigen, treatment arm, and timepoint will be made. For all primary and secondary immunogenicity endpoints, box plots and plots of estimated reverse cumulative distribution curves will be used for graphical display of all of the study arms. Typically, the results will be shown for each vaccine arm and for the set of control arms pooled into one group.

The differences between treatment groups at 2 weeks post the 2nd and 4th vaccination timepoints will be tested with a nonparametric Wilcoxon rank sum test if the data are not normally distributed and with a 2-sample t-test if the data appear to be normally distributed.

Some immunologic assays have underlying continuous or count-type readouts that are dichotomized into responder/nonresponder categories (eg, ICS and BAMA). If treatment arm differences for these assays are best summarized by a mixture model, then Lachenbruch's test statistic [93] will be used to evaluate the composite null hypothesis of equal response rates in the 2 arms and equal response distributions among responders in the 2 such arms. This test statistic equals the square of a binomial Z-statistic for comparing the response rates plus the square of a Wilcoxon statistic for comparing the response rates plus the square of a P-value. For estimation, differences in response rates between arms will be estimated using the methods described above, and in the subgroup of positive responders, differences in location parameters between arms will be estimated using the methods described above.

More sophisticated analyses employing repeated measures methodology (eg, linear mixed models or marginal mean models fit by generalized estimating equations) may be utilized

to incorporate immune responses over several timepoints and to test for differences over time. However, inference from such analyses would be limited by the small sample size of this study. All statistical tests will be 2-sided and will be considered statistically significant if $p \le 0.05$.

Based upon previous HVTN trials, missing 17% of immunogenicity results for a specific assay is common due to study participants terminating from the study early, problems in shipping specimens, or low cell viability of processed peripheral blood mononuclear cells (PBMCs). To achieve unbiased statistical estimation and inferences with standard methods applied in a complete-case manner (only including participants with observed data in the analysis), missing data need to be missing completely at random (MCAR). Following the most commonly used definition, MCAR assumes that the probability of an observation being missing does not depend on any participant characteristics (observed or unobserved). When missing data are minimal (specifically if no more than 20% of participants are missing any values), then standard complete-case methods will be used, because violations of the MCAR assumption will have little impact on the estimates and hypothesis tests.

If a substantial amount of immunogenicity data is missing for an endpoint (at least 1 value missing from more than 20% of participants), then using the methods that require the MCAR assumption may give misleading results. In this situation, analyses of the immunogenicity endpoints at a specific timepoint will be performed using parametric generalized linear models fit by maximum likelihood. These methods provide unbiased estimation and inferences under the parametric modeling assumptions and the assumption that the missing data are missing at random (MAR). MAR assumes that the probability of an observation being missing may depend upon the observed responses and upon observed covariates, but not upon any unobserved factors. Generalized linear models for response rates will use a binomial error distribution and for quantitative endpoints, a normal error distribution. For assessing repeated immunogenicity measurement, linear mixed effects models will be used. If the immunological outcomes are left- and/or rightcensored, then the linear mixed effects models of Hughes [94] will be used, because they accommodate the censoring. In addition, secondary analyses of repeated immunogenicity measurements may be done using weighted GEE [95] methods, which are valid under MAR. All of the models described above in this paragraph will include as covariates all available baseline predictors of the missing outcomes.

6.4.4.2 Analysis of CD4⁺ and CD8⁺ T-cell response as measured by the ICS assay

The analysis of CD4⁺ and CD8⁺ T-cell response rates as measured by the ICS assay will be evaluated and compared as described under the general approach. For each T-cell subset, the positivity call for each peptide pool will include a multiple comparison adjustment for the number of peptide pools used in the assay. In general, the Mixture Models for Single-cell Assays (MIMOSA) statistical framework [96] and/or the Fisher's exact test-based positivity criteria will be used. Details of the positivity criteria will be discussed in the SAP. The magnitude of marginal response will be analyzed as described for quantitative data in the general approach section. For each T-cell subset, graphs will be used to display the background-subtracted magnitudes for each participant by protein, treatment arm and timepoint. Statistical testing comparing the magnitudes will be based on positive responders only. The polyfunctionality of ICS responses will also be analyzed as a secondary endpoint. Besides descriptive plots of the magnitude of polyfunctional responses, the COMPASS (Combinatorial Polyfunctionality analysis of Antigen-Specific T-cell Subsets) statistical framework will also be used to perform joint modelling of

multiple T-cell subsets of different cytokine combinations using the functionality score (FS) and the polyfunctionality score (PFS) to summarize the multi-parameter ICS responses.

